### 1.5.2. EFFICACY ASSESSMENT

#### Objective response rate (ORR)

This will be assessed according to RECIST version 1.1 criteria, to be performed every 8 weeks, regardless of treatment delays caused by treatment toxicity.

The ORR is defined as the percentage of patients in which there is confirmation of a complete response (CR) or a partial response (PR) according to RECIST criteria, in relation to the total analysis population.

A response is confirmed for patients in whom the response persists in an imaging test repeated  $\geq 4$  weeks after initial documentation of response.

#### Progression-free survival (PFS)

This is defined as the time between the start of study treatment to the date of first objective evidence of radiological progression or patient death from any cause; whichever comes first.

#### Time to progression (TTP)

This is defined as the time between the start of study treatment to the date of first objective evidence of radiological progression.

#### Response duration (RD)

This is defined as the time between the first recorded objective response (CR or PR), which is subsequently confirmed, to the first objective evidence of radiological progression or death from any cause.

RD will only be calculated in the subgroup of patients with objective response (CR + PR).

### Overall survival (OS)

This is defined as the time between the start of study treatment to the date of death from any cause.

If confirmation of death could not be obtained, survival will be censored with the date of the last visit at which time the patient was known to be alive.

### Safety

See Safety Assessment section below.

### Biomarkers:

They assess the correlation between radiological response and the patient's clinical course and the following expression levels:

- ENO1 (enolase 1) in plasma (it will be performed locally at the same time as chromogranin at each participating site)
- SNPs (single nucleotide polymorphisms) related to the activity and metabolism of sunitinib and TH-302 VEGFR2 (rs2305948 and rs1870377), VEGFR3 (rs307826), IL8 (rs1126647), CYP3A4 (rs35599367 and rs67666821), CYP3A5 (rs776746), ABCB1 (rs1045642, rs1128503 and rs2032582), POR (rs1057868 and c.1705\_1706insG). If a polymorphism of particular relevance and related to the effectiveness of sunitinib or TH-302 appears in the literature as the study progresses, its inclusion in the study could be considered.
- Hypoxia markers related to paraffin-embedded tumour tissue (HIF1-  $\alpha$ , CYP2W1 and c-Myc).

### 1.5.3. SAFETY ASSESSMENT

The safety period runs from the date of the signature of the informed consent form until 28 days after the last dose of the study drug. Safety will be evaluated according to adverse event reports, the frequency of treatment discontinuations due to adverse events, and laboratory or ECG tests. Descriptive analysis will be used.

### Adverse Events

An adverse event is defined as any unwanted or unintended symptom, sign, disease or experience (including a clinically significant laboratory result of any grade according to the common terminology criteria for adverse events [CTCAE] of the National Cancer Institute, version 4.0) that emerges or worsens during the course of the study, whether related or not to the study drug.

### 1.5.4. DETERMINATION OF SAMPLE SIZE

It is estimated that a total of 43 eligible patients will be enrolled in the study (having received at least one dose of treatment). The design will follow Simon's two-stage design for phase II studies, with a baseline number of 18 patients. The combination of TH-302 with sunitinib will be considered as inactive in terms of the response rate if less than 5% of patients are

responders, with a response rate threshold of 20%. These figures are based on the results shown with other drugs for the treatment of pNET.

Should a response be identified in at least 3 out of every 18 patients treated, recruitment will continue up to 43 patients in order to be able to better estimate the response rate. If the study shows a response in at least 8 patients, the treatment is likely to continue its research development.

The likelihood of terminating the study after the first part with 18 patients enrolled is 0.42 if the response rate is 10%, and 0.06 if the response rate is 25%.

The likelihood of not accepting the null hypothesis and considering the combination of TH-302 with sunitinib active with a response rate less than 5% is 5% (Type I or alpha error).

The likelihood of not rejecting the null hypothesis and considering the combination of TH-302 with sunitinib inactive with a response rate greater than 5% is 20% (Type II or beta error). The statistical power of the study will be 0.80.

### 1.5.5. METHODS OF STATISTICAL ANALYSES

#### 1.5.5.1 Descriptive analysis

The descriptive analysis of patient characteristics will include demographic data, disease-specific data and prior treatments. Qualitative data will be described with absolute frequencies and corresponding percentages. Quantitative data will be studied using the mean  $\pm$  standard deviation, median, minimum and maximum values. The response percentages will be estimated using confidence intervals of 95%.

In the safety analysis, adverse events will be specified according to the maximum grade described at the discretion of the investigator and defined by NCI-CTCAE, version 4.0, including adverse events described from treatment initiation until 28 days following its completion.

The following safety analysis data will be presented:

- Temporary and permanent treatment discontinuations due to an adverse event.
- Deaths.
- Adverse Events (AEs) and Serious Adverse Events (SAEs).
- Hospitalisations.
- Use of concomitant medication and growth factors.

#### 1.5.5.2 Primary Efficacy analysis

##### Objective response rate (ORR).

The objective response rate corresponding to the percentage of patients in which there is confirmation of a complete response (CR) or a partial response (PR) according to RECIST criteria, in relation to the total analysis population, will include a confidence interval of 95%.

### 1.5.5.3 Secondary Efficacy analysis

The secondary efficacy objectives of the study are:

- Progression-free survival
- Time to tumour progression
- Duration of response
- Overall survival
- Prognostic/predictive value of biomarkers analysed in peripheral blood and in paraffin-embedded tumour tissue.

The survival analyses will be performed using the Kaplan-Meier method presented with the corresponding graph, as well as by Cox regression analysis to obtain the hazard ratios and confidence intervals for the associations. For patients without documented progression or death at the time of analysis, the PFS will be censored at the last date of tumour assessment. For patients who have not died at the time of analysis, the OS will be censored.

The association between the marker expression profiles analysed in plasma and treatment response (yes/no) will be assessed using logistic regression models and univariate and multivariate Cox regression, establishing the corresponding hazard ratio and confidence interval at 95%. The predictive value (of genetic biomarkers, in plasma and tumour tissue) of each model will be estimated using an area under the ROC curve.

All statistical tests are bilateral, two-tailed tests, and all values with  $p < 0.05$  will be considered significant.

### 1.5.5.4 Safety analysis

**Safety of TH-302 treatment in combination with sunitinib**

Adverse events and serious adverse events, laboratory test results, physical examination findings and vital signs, and their changes from baseline will be summarized using descriptive statistics. Abnormal values will be flagged.

### 1.5.6. INTERIM ANALYSES

There are no efficacy interim analyses planned on the primary endpoint because all secondary variables and safety at the end of the treatment period and during the follow-up period will be evaluated.

### 1.5.7. RECORDING OF DATA

An Electronic Data Capture (EDC) System will be used for data collection and query handling. The investigator will ensure that data are recorded on the eCRF as specified in the study protocol and in accordance with the instructions provided.

The investigator ensures the accuracy, completeness, and timeliness of the data recorded and of the provision of answers to data queries according to the GCPs.

## 2. RESULTS

### 2.1. STUDY POPULATION

#### 2.1.1. Recruited patients (centres/investigators)

Initially **XXX patients** were recruited in XXX Spanish sites. The recruited period lasted from **xxxxxx 20xx** until **xxxxxx 20xx**. The distribution of patients by centres will be shown in the following table:

Table 1. Recruited patients by site

Centre	Investigator	Patients N (%)
Total		xx (100.0)

Moreover **XXX patients** were screened without being finally recruited for the study.

#### 2.1.2. Evaluable patients

Following protocol indications it was analysed which patients could be included in the analysis:

General inclusion criteria:

- Patients over 18 years with performance status ECOG 0 or 1.
- Obtaining informed consent in writing and signed.
- Pancreatic neuroendocrine tumours (pNET) diagnosed histologically with a Ki67 ≤ 20% (well- or moderately-differentiated tumours).
- Evidence of unresectable or metastatic disease. Locally advanced disease must not be amendable to surgical resection or radiation therapy with curative intent.
- Prior systemic therapy is not permitted. Patients may be treated with somatostatin analogues prior to or during the trial. Concomitant or prior interferon (IFN) treatment is not permitted.
- Adequate hematologic, hepatic, renal and cardiac function

In the following table the number of non evaluable patients along with the reason why, will be reported.

**Table 2. Non evaluable patients**

No.	ID patient	Hospital	Reason

The population by sites will be described in **Table 3**:

**Table 3. Patients evaluable by Site**

	Total
	N (%)
Hospital 1	
Hospital 2	
...	
Total	xx (100.0)

In this report, data from **xxx patients from xx** Spanish sites will be analysed. A database cut-off was made in **xxxxxx 2017** for this 1st preliminary analysis.

**Table 4. Evaluable patients**

	n	% 
Total number of recruited patients		100,0

**Recruited**

- *Patients over 18 years with performance status ECOG 0 or 1.*
- *Obtaining informed consent in writing and signed.*
- *Pancreatic neuroendocrine tumours (pNET) diagnosed histologically with a Ki67  $\leq$  20% (well- or moderately-differentiated tumours).*
- *Evidence of unresectable or metastatic disease. Locally advanced disease must not be amendable to surgical resection or radiation*

therapy with curative intent.

- Prior systemic therapy is not permitted. Patients may be treated with somatostatin analogues prior to or during the trial. Concomitant or prior interferon (IFN) treatment is not permitted.
- Adequate hematologic, hepatic, renal and cardiac function

---

### Total number of non recruited patients

- Exclusion criteria
- 

 Calculated percentage from the total of patients with available data

## 2.2. BASELINE PATIENT CHARACTERISTICS

For the descriptive analysis of the patients, the evaluable population will be used (see section 2.1).

The mean age of the women included in the study was XXXX years.

**Table 5. Baseline patient characteristics**

Sociodemographic	N	Mean (SD)	Median (Min-Max)
Age			
			N (%)
Gender	Male		
	Female		
Race	White		
	Black		
	Hispanic		
	Asian		
	Other		
Vital signs			N (%)
Performance status	0		
	1		
	N	Mean (SD)	Median (Min-Max)
Body weight			
Height			
BMI			
Body area			
Systolic Blood pressure			
Diastolic Blood pressure			
	Basal comorbidity		N (%)
Charlson	0		
	1		
	2		
	≥3		
Cerebral vascular disease	Normal		
	Abnormal		
Peripheral arterial disease	Normal		
	Abnormal		
Diabetes	Normal		
	Abnormal		

---

Heart failure/ ischemic heart disease	Normal	
	Abnormal	
Dementia	Normal	
	Abnormal	
Chronic renal failure	Normal	
	Abnormal	
Cancer	Normal	
	Abnormal	
Chronic obstructive pulmonary disease	Normal	
	Abnormal	
	Electrocardiogram (ECG)	N (%)
	<450 mseg	
	450-480 mseg	
QT interval corrected	481-500 mseg	
	>501 mseg	
	Others	
	Echocardiogram /MUGA	N (%)
LVEF	<50%	
	≥50%	

Table 6. Baseline analytics

Haematology	N	Mean (SD)	Median (Min-Max)
Haemoglobin (g/dL)			
White blood cells (x10  /L)			
Absolute neutrophil count (x10  /L)			
Absolute Lymphocytes count (x10  /L)			
Platelet count (x10  /L)			
Biochemical	N	Mean (SD)	Median (Min-Max)
Sodium (mmol/L)			
Potassium (mmol/L)			
Calcium(mmol/L)			
Magnesium (mmol/L)			
Glucose (mmol/L)			
Creatinine (mg/dL)			
Aspartate AST (SGOT)			
Alanine transaminase ALT (SGPT)			
AST (SGOT)/ ALT (SGPT)			
Total bilirubin (mg/dL)			
Gamma-glutamyltransferase (GGT)			
Alkaline phosphatase (AP)			
Albumin (mg/dL)			
Lactate dehydrogenase [LDH]			
Blood clotting	N	Mean (SD)	Median (Min-Max)
Prothrombin time (PT)			
Activated Partial Thromboplastin Time (aPTT)			
Thyroid function	N	Mean (SD)	Median (Min-Max)
Thyroid-Stimulating Hormone (TSH)			
T4			
Tumour markers	N	Mean (SD)	Median (Min-Max)

Cg A

Enolase 1

### 2.3. TUMOR DATA AND PRIOR TREATMENTS

Baseline tumour characteristics will be reported in this section.

**Table 7. Tumour characteristics**

	N (%)		
Histological grade	G1 – Well differentiated		
	G2 – Moderately differentiated		
	Unknown		
Ki-67 Index	≤2%		
	>2-5%		
	>5-10%		
	>10%		
Mitosis 10 CGA	<2		
	2-20		
Type of tumour	Functioning		
	Not functioning		
Histological subtype	Gastrinoma		
	Glucagonoma		
	Insulinoma		
	VIPoma		
	Somatostatinoma		
	Others, multisecretor or unknown		
Surgery	Yes		
	No		
Stage at diagnosis	I		
	II		
	III		
	IV		
CT relapse	Yes		
	No		
Relapse location	Hepatic		
	Extra-hepatic		
	N	Mean (SD)	Median (Min-Max)
Time between diagnosis (anatomical pathology) and treatment initiation			
Time between diagnosis (anatomical pathology) and surgery			
Time between diagnosis (anatomical pathology) and CT relapse			
Somatostanine analogues prior the trial	Yes		
	No		

## 2.4. CONCOMITANT MEDICATION

In this section concomitant medications will be shown.

**Table 8. Concomitant medication**

		N (%)
Concomitant medication	No	
	Yes	
Concomitant medications	Concomitant medication 1	
	Concomitant medication 2	
	Concomitant medication 3	
	...	

## 2.5. TREATMENT EXPOSURE

The TH-302 dose administered will be 340 mg/m^2 by intravenous infusion over 30-60 minutes, on days 8 and 22 of each cycle. The dose should be adjusted according to body surface area. In the event of patient weight variation > 10%, the body surface area will be recalculated and the TH-302 dose readjusted.

Details of TH-302 compliance will be shown in the following table:

**Table 9. TH-302 compliance**

	N	Mean (SD)	Median (Min-Max)
Number of TH-302 cycles			
Length of TH-302 treatment (weeks)			
			N (%)
Total number of cycles with TH-302	1 cycle		
	2 cycles		
	3 cycles		
	4 cycles		
	5 cycles		
	6 cycles		
	...		
Total number of TH-302 reductions	1 reduction		
	2 reductions		
	3 reductions		
	4 reductions		
	...		
Reason for TH-302 reductions	Reason 1		
	Reason 2		
	Reason 3		
	...		
Total number of TH-302 delays	1 delay		
	2 delays		
	3 delays		
	4 delays		
	...		
Reason for TH-302 delays	Reason 1		
	Reason 2		

	Reason 3		
	...		
Total number of TH-302 omissions	1 omission		
	2 omissions		
	3 omissions		
	4 omissions		
	...		
Reason for TH-302 omissions	Reason 1		
	Reason 2		
	Reason 3		
	...		
	N	Mean (SD)	Median (Min-Max)
Length of TH-302 temporary interruption (weeks)			

If any patient did not receive TH-302 it will be listed below along with her details.

**Table 10. List of patients that did not receive TH-302**

Patient ID code	Total number of TH-302 cycles	Date of cycle 1	Date of cycle 2	Date of cycle 3	Date of cycle 4	Date of cycle 5	Date of cycle 6
	0						

Sunitinib will be administered at a dose of 37.5 mg per day (1 capsule of 25 mg and 1 capsule of 12.5 mg) orally for 28 days on an ongoing basis. It must always be taken at the same time every day (or as close as possible) and capsules must be swallowed whole.

Details of Sunitinib compliance will be shown in the following table:

**Table 11. Sunitinib compliance**

	N	Mean (SD)	Median (Min-Max)
Number of Sunitinib cycles			
			N (%)
Total number of cycles with Sunitinib	1 cycle		
	2 cycles		
	3 cycles		
	4 cycles		
	5 cycles		
	6 cycles		
Total number of Sunitinib reductions	1 reduction		
	2 reductions		
	3 reductions		
	4 reductions		
	5 reductions		
	6 reductions		
Reason for Sunitinib reductions	Reason 1		
	Reason 2		
	Reason 3		
	...		
Total number of Sunitinib delays	1 delay		
	2 delays		

	3 delays		
	4 delays		
	5 delays		
	6 delays		
Reason for Sunitinib delays	Reason 1		
	Reason 2		
	Reason 3		
	...		
Total number of Sunitinib omissions	1 omission		
	2 omissions		
	3 omissions		
	4 omissions		
	5 omissions		
	6 omissions		
Reason for Sunitinib omissions	Reason 1		
	Reason 2		
	Reason 3		
	...		
	N	Mean (SD)	Median (Min-Max)
Length of Sunitinib temporary interruption (weeks)			

If any patient did not receive Sunitinib it will be listed below along with her details.

**Table 12. List of patients that did not receive Sunitinib**

Patient ID code	Total number of Sunitinib cycles	Date of cycle 1	Date of cycle 2	Date of cycle 3	Date of cycle 4	Date of cycle 5	Date of cycle 6
	0						

### 2.5.1. Withdrawal of patients from therapy or assessment

Treatment with TH-302 in combination with sunitinib will continue until disease progression, unacceptable toxicity, non-compliance with the protocol, the patient's withdrawal of informed consent or at the discretion of the investigator. In case of withdrawal of the study medication for toxicity, the patient will continue follow-up according to the scheduled study activities, and the investigator following the patient shall be responsible for initiating another systemic treatment option if deemed appropriate.

If any patient stopped the study treatment prematurely, it will be listed below along with her details.

**Table 13. Study treatment premature interruption**

	N (%)
Study treatment premature interruption	Yes
	No
Reasons for study treatment premature interruption	Reason 1
	Reason 2
	Reason 3
	...

If any patient did not receive Sunitinib/TH-302 during any cycle, it will be listed below along with her details.

**Table 14. List of patients that did not receive Sunitinib/TH-302**

Patient ID code	Reason for premature interruption

Details of the end of treatment reasons will be shown in the following table.

**Table 15. Reason for end of treatment**

		N (%)	
Reasons for end of treatment	Progression		
	Unaccepted toxicity		
	Details of toxicities	Toxicity 1	
		Toxicity 2	
		...	
	Investigator decision		
	Details of investigator decisions	Investigator decision 1	
		Investigator decision 1	
	...		
	Other reasons		
Details of other reasons	Other reasons 1		
	Other reasons 2		
...			

The median of the study treatment was XXX weeks:

**Table 16. Study treatment length**

	N	Mean (SD)	Median (Min-Max)
Length of study treatment (weeks)			

## 2.6. ANALYSIS SETS

All safety and efficacy analyses will be based in the total analysis population. Any patient fulfilling all the inclusion criteria and none of the exclusion criteria will be included the total analysis population.

**Table 17. Analysis sets**

		N (%)
Total analysis population	Yes	
	No	
Reason excluded	Reason 1	
	Reason 2	
	....	

If any patient is excluded from the total analysis population, it will be listed below along with the reasons why:

**Table 18. List of patients that are excluded total analysis population**

Patient ID code	Total analysis population	Reason excluded from total analysis population

## 2.7. EFFICACY ANALYSIS

The total analysis population will be used to present the efficacy analysis.

### 2.7.1. Primary efficacy analysis

#### Objective response rate (ORR)

[figure not shown]
The objective response rate (ORR) will be reported with absolute and relative frequencies and using the binomial test procedure their 95% confidence interval (CI95%) will be provided. According to the protocol the ORR is defined as the percentage of patients in which there is confirmation of a complete response (CR) or a partial response (PR) according to RECIST criteria, in relation to the total analysis population.

In the total analysis population (n=XX), the objective response rate, disease control rate and CA 125 rate will be detailed below:

**Table 19. Response**

	N (%; IC 95%)
Response rate according to RECIST	Complete response (CR)
	Partial response (PR)
	Stable disease (SD)
	Progression disease (PD)
	Total
Objective response rate: CR or PR according to RECIST	Yes
	No
	Total
Disease-control rate: CR or PR o SD according to RECIST	Yes
	No
	Total

Figure 4 Waterfall plot: Maximum % change from baseline in target tumor measurement for each patient

In those patients that responded (CR or PR according to RECIST) the “time to response” will be calculated. This is defined as the time between date of treatment initiation and the first recorded objective response (CR or PR), which is subsequently confirmed.

The median of the time to response was XXX weeks:

**Table 20. Time to response**

	N	Mean (SD)	Median (Min-Max)
Time to response (weeks)			

### 2.7.2. Secondary efficacy analysis

The progression free survival will be estimated and plotted using the Kaplan-Meier product-limit method, along with their corresponding log-log transformed 95% confidence intervals

Time to tumour progression, duration of response and overall survival will also be described using these same Kaplan-Meier methods.

Cox regression analysis will be used to obtain hazard ratios and their confidence intervals for the associations. For patients without documented progression or death at the time of analysis, the PFS will be censored at the last date of tumour assessment. For patients who have not died at the time of analysis, the OS will be censored.

The association between the marker expression profiles analysed in plasma and treatment response (yes/no) will be assessed using logistic regression models and univariate and multivariate Cox regression, establishing the corresponding hazard ratio and confidence interval at 95%. The predictive value (of genetic biomarkers, in plasma and tumour tissue) of each model will be estimated using an area under the ROC curve.

#### 2.7.2.1 Progression Free Survival

The progression-free survival rate will be estimated and plotted using the Kaplan-Meier product-limit method, along with their corresponding log-log transformed 95% confidence intervals.

In the total analysis population (n=XX), at 3 months the proportion of patients that survived without PD or exitus was XXXX with a 95% CI XXXX-XXXX. The overall median of PFS was XXX months (95% CI XXX-XXX).

**Table 21. Progression free survival**

PFS	N events	Patients at risk	% estimated cumulative survival ratio 	95% CI	% with PD
at 3 months					
at 6 months					
at 12 months					
	N	N (%) events	Median (months)	Standard error	95% CI
Estimated PFS					

[figure not shown]
1: Estimated using Kaplan-Meier product-limit method

**Table 22. Progression free survival events**

PFS event	N (%; IC 95%)	
	Without PD/Exitus	
	PD	
	Exitus (without previous PD)	
Total		

**Figure 5 Kaplan Meier curve: PFS**

**2.7.2.2 Time to tumour progression**

The time to tumour progression will be calculated in those patients with objective evidence of radiological progression. This is defined as the time between the start of study treatment to the date of first objective evidence of radiological progression.

The median of the time to tumour progression was XXX weeks:

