9. STATISTICAL ANALYSIS

9.1. *Descriptive Analysis*

The descriptive analysis of patient characteristics will include demographic data, disease-specific data and prior treatments. Qualitative data will be described with absolute frequencies and corresponding percentages. Quantitative data will be studied using the mean \pm standard deviation, median, minimum and maximum values. The response percentages will be estimated using confidence intervals of 95%. In the safety analysis, adverse events will be specified according to the maximum grade described at the discretion of the investigator and defined by NCI-CTCAE, version 4.0 (see section 10.2.3.), including adverse events described from treatment initiation until 28 days following its completion.

The following safety analysis data will be presented:

- Temporary and permanent treatment discontinuations due to an adverse event.
- Deaths.
- Adverse Events (AEs) and Serious Adverse Events (SAEs).
- Hospitalisations.
- Use of concomitant medication and growth factors.

9.2. *Inferential Analysis*

The objective response rate corresponding to the percentage of patients in which there is confirmation of a complete response (CR) or a partial response (PR) according to RECIST criteria, in relation to the total analysis population, will include a confidence interval of 95%. The association between the marker expression profiles analysed in plasma and in tumour tissue for treatment response (yes/no) will be assessed using logistic regression models and univariate and multivariate Cox regression, establishing the corresponding *hazard ratio* and confidence interval at 95%. The predictive value (of genetic biomarkers, in plasma and tumour tissue) of each model will be estimated using an area under the ROC curve.

The survival analyses will be performed using the Kaplan-Meier method presented with the corresponding graph, as well as by Cox regression analysis to obtain the *hazard ratios* and confidence intervals for the associations. For patients without documented progression or death at the time of analysis, the PFS will be censored at the last date of tumour assessment. For patients who have not died at the time of analysis, the OS will be censored.

All statistical tests are bilateral, two-tailed tests, and all values with $p < 0.05$ will be considered significant.

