**Table 23. Time to tumour progression**

	N	Mean (SD)	Median (Min-Max)
Time to tumour progression (weeks)			

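### SAP 2.7.2.2 and Table 23 compute time to progression only in patients who progressed, against the Kaplan-Meier method set in SAP 2.7.2; if followed, TTP is biased short

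*SAP*

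**What the plan says.** Both documents define TTP without restricting who contributes (protocol 10.1, SAP 1.5.2): it runs from start of treatment to first radiological progression. Protocol 9.2 and SAP 1.5.5.3 set the general method: "The survival analyses will be performed using the Kaplan-Meier method presented with the corresponding graph". SAP 2.7.2, which introduces all secondary efficacy results, names TTP: "Time to tumour progression, duration of response and overall survival will also be described using these same Kaplan-Meier methods".

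SAP 2.7.2.2 departs from this: "The time to tumour progression will be calculated in those patients with objective evidence of radiological progression". The results sentence is "The median of the time to tumour progression was XXX weeks". Table 23 offers N, mean (SD) and median (min-max). It has no column for events, no confidence interval and no Kaplan-Meier footnote.

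PFS is handled differently. Its sentence is "The overall median of PFS was XXX months", with a confidence interval. Table 21 gives events, patients at risk and 95% CI, footnoted "Estimated using Kaplan-Meier product-limit method". SAP 1.5.5.3 and 2.7.2 state how PFS and OS are censored; neither gives a rule for TTP.

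**The concern.** The two instructions cannot be reconciled by running Kaplan-Meier on the set named in 2.7.2.2. Everyone in that set has the event, so nobody is censored and the curve is simply the raw distribution among progressors. The sentence and the table shell agree with each other, so a programmer filling the shells would produce that raw summary.

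The patients left out are those still progression-free at cut-off and those in the Table 22 row for death without earlier progression. The first group has TTP longer than its follow-up, so removing it removes long times. The result is short whenever anyone is progression-free at cut-off.

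It would also sit beside a correctly estimated PFS. TTP events are a subset of PFS events. On the same patients, with deaths censored when they occur, the Kaplan-Meier TTP curve cannot lie below the PFS curve. The planned shells could nevertheless show a TTP median below the PFS median. With TTP in weeks and PFS in months, a reader might not notice.

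**Working it through.** The plan gives no TTP figure to reproduce, because the results are placeholders. The size of the bias is therefore an illustration.

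**Inputs from the documents**
- 43 patients (protocol 5.4, SAP 1.5.4).
- 24 months of accrual and 20 of follow-up (protocol 5.3), so T = 44 months.
- Median m = 7.7 months: TTP in the phase II sunitinib study (protocol 3.3), the only TTP median in the documents.
- m = 11.4 months: PFS in the phase III sunitinib study (protocol 3.3), as a stand-in.
- m = 18 months: PFS in the retrospective temozolomide-capecitabine review (protocol 3.2), a different regimen, as a stand-in.

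**Assumptions**
- Exponential times, uniform accrual and administrative censoring.
- Deaths without progression are a share f of PFS events, with f = 0, 10% or 20%, independent of progression. The documents give no figure for f.

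**Formulas**
- Progression hazard: λ = ln 2 / m. Total hazard: L = λ/(1−f).
- Average share still event-free at cut-off: S = (e^(−20L) − e^(−44L)) / (24L).
- Share with observed progression: P = (1−f)(1−S).
- Every patient has at least 20 months of potential follow-up. For t up to 20 months, the share progressed by t is therefore (1−f)(1−e^(−Lt)). Setting this to P/2 gives the progressors-only median: t = −ln[1 − P/(2(1−f))] / L.

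**Worked case, m = 7.7, f = 0**
- λ = 0.0900.
- S = (0.1652 − 0.0190) / (24 × 0.0900) = 0.068, so P = 0.932.
- t = −ln(1 − 0.466) / 0.0900 = 6.97 months.
- Shortfall: 1 − 6.97/7.7 = 9.4%.

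**Large-sample results at 44 months**

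| True median | f | Share progressed | Progressors-only median | Shortfall |
|---|---|---|---|---|
| 7.7 | 0 | 0.93 | 6.97 | 9.4% |
| 7.7 | 10% | 0.85 | 6.43 | 16.5% |
| 7.7 | 20% | 0.77 | 5.84 | 24.1% |
| 11.4 | 0 | 0.84 | 9.02 | 20.9% |
| 11.4 | 10% | 0.79 | 8.48 | 25.7% |
| 11.4 | 20% | 0.72 | 7.86 | 31.1% |
| 18 | 0 | 0.70 | 11.14 | 38.1% |
| 18 | 10% | 0.66 | 10.69 | 40.6% |
| 18 | 20% | 0.62 | 10.16 | 43.6% |

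At the January 2019 study end (47 months from February 2015) with f = 0, the shortfalls are 7.3%, 17.6% and 34.4%.

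The mean in Table 23 is low too. In simulated trials with f = 0 it is typically 9.0, 11.0 and 12.9 months, against true means (m / ln 2) of 11.1, 16.4 and 26.0.

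**Preliminary cut-off.** SAP 2.1.2 refers to a 2017 database cut-off with the month blank. With m = 7.7, f = 0 and a first patient in February 2015, the progressors-only median is 4.32 months at 24 months (43.8% short), 5.32 at 30 (30.9%) and 5.99 at 34 (22.2%).

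**Comparison with PFS.** In simulated trials of 43 patients at 44 months, the share in which the progressors-only TTP median falls below the same trial's Kaplan-Meier PFS median is:

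| True median | f = 0 | f = 10% | f = 20% |
|---|---|---|---|
| 7.7 | 95% | 75% | 62% |
| 11.4 | over 99% | 95% | 85% |
| 18 | over 99% | over 99% | 99% |

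These shares count any difference. At m = 7.7 the median gap is only about 0.5, 0.3 and 0.2 months for f = 0, 10% and 20%.

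**The case against.** The strongest reply is that the right method is already in the plan. Section 2.7.2 names TTP and sets Kaplan-Meier, the definitions contain no restriction, and the SAP does not say that a subsection overrides its parent. The fault is one sentence and one shell in a results template that carries other leftovers, such as a CA 125 rate in 2.7.1 and a reference to the women's mean age in 2.2. That is fair, and it is why the bias is conditional on 2.7.2.2 being followed. But two analysts could then report different numbers for a named secondary endpoint, and an SAP should settle that before the data are seen.

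The second reply is that the effect is small. At 7.7 months with no deaths it is about 0.7 months (7.7 − 6.97), while single-trial Kaplan-Meier medians at n = 43 range from 4.9 to 11.5 months (2.5th to 97.5th percentiles). The larger shortfalls rest on PFS stand-ins, one from a different regimen, or on assumed death shares. With 20% deaths at 7.7 months, the order of the TTP and PFS medians often reverses. All of this stands as a limit on size. It does not change the direction of the bias from dropping progression-free patients, and a systematic error does not average out.

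Third, PFS is planned correctly and Table 22 separates progression from death, so the report would still contain a valid related estimate. That limits the harm but does not make the TTP figure right.

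**Conclusion.** The concern holds. Sections 2.7.2 and 2.7.2.2 contradict each other in current text, and the version carried into the table shell gives a wrong result. Under the stated assumptions, the progressors-only median at 44 months is 9% short for the documents' own TTP median of 7.7 months. It is 21% and 38% short for the PFS stand-ins of 11.4 and 18 months. Deaths before progression and an earlier cut-off increase the shortfall. The size depends on exponential times, uniform accrual, borrowed medians and, where f is above zero, independent deaths. The downward direction needs only that some patients are progression-free at cut-off. TTP is secondary with no decision rule, so the ORR decision is untouched. It should be fixed before analysis.

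**What to change.** - Rewrite SAP 2.7.2.2 as a Kaplan-Meier analysis of the total analysis population. Censor patients without radiological progression at their last tumour assessment, as SAP 1.5.5.3 does for PFS.
- State how deaths without progression are handled. Applying the same censoring is one standard choice.
- Replace Table 23 with N, N (%) events, Kaplan-Meier median and 95% CI, following the lower part of Table 21, and report in the same time unit as PFS.
- As a minor consistency edit, give Table 24 (response duration) the same columns, with ongoing responses censored as for PFS. Section 2.7.2 sets Kaplan-Meier for response duration too, and restricting it to responders is correct.

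The cost is SAP wording, one table shell and a small edit to a second. No new data are needed.
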